	
approach. These analyses will be conducted sequentially, starting from the first objective with progression towards the fifth objective. Each subsequent objective is only analyzed when all of the previous analyses are successful at demonstrating superiority.
 
Additional Observations Analysis
 
Traditional confidence intervals and p-values will be reported for these analyses, as applicable.
 
 • Knee Range of Motion (ROM) – evaluation using Calypso Knee System at baseline compared to 24 months • Adverse Events by type over time, severity, seriousness, and relatedness. AEs will be tabulated and summarized as counts and percentages. AEs will also be cross-tabulated according to: 
 ○ Severity; ○ Unanticipated Adverse Device Effect (UADE) ○ Seriousness (Serious Adverse Event (SAE), Non-serious AE); ○ Device-Relatedness (Unrelated, Possibly Related, Probably Related, Definitely Related); ○ Procedure-Relatedness (Unrelated, Possibly Related, Probably Related, Definitely Related). • Secondary surgical interventions by type of surgical intervention (revision, removal, re-operation (includes conversion to arthroplasty) supplemental fixation, other intervention) • Changes in patient reported knee outcome measures and activity (KOOS Knee Survey, KSS, Subject Activity and Satisfaction, SF-12 Health Survey) as compared to baseline • Changes in Investigator reported KSS
Study Duration:	All subjects included in this study will return for follow-up visits at 6 weeks and 3, 6, 12, 18, and 24 months, then annually through 5 years.
References:	
CLIN102840: Calypso Knee System Metal Ion Protocol LBL102812: Calypso Knee System, Instructions for Use - Product Insert LBL102811: Calypso Knee System Instruments, Instructions for Use - Product Insert CLIN102845: Calypso Knee System Surgical Technique Guide CLIN102792: Calypso Clinical Study Radiographic Evaluation Protocol CLIN102799: Calypso Clinical Study Informed Consent CLIN102852: Calypso Clinical Study Implant Retrieval Protocol CLIN102838: Calypso Knee System Rehabilitation Guideline CLIN102842: Calypso Clinical Study Investigator’s Agreement CLIN103113: Statistical Considerations and Preliminary Propensity Score (PS) Design Memorandum CLIN102839: Calypso Clinical Study Surgeon Training CLIN102853: Calypso Clinical Study Monitoring Plan CLIN102859: Calypso Clinical Study CEC Charter

Calypso Knee System Clinical Study

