2.1.1 Study Design Overview

The Calypso Clinical Study is a prospective, multicenter clinical study comparing the Calypso Knee System to the cohort of subjects treated with High Tibial Osteotomy (HTO) from a recent non-randomized trial (GOAL study). A total of 80 subjects will be enrolled in this study at up to 10 investigational sites located in the U.S. using a staged enrollment.

[REDACTED]

The subject population for this study is male or female subjects age 25 to 65 years, with a diagnosis of medial knee osteoarthritis and study knee pain with an overall WOMAC pain score ≥ 40 (scale 0-100).

All subjects included in this study will return for follow-up visits at 6 weeks and 3, 6, 12, 18, and 24 months, then annually through 5 years.

At each follow-up visit, safety and effectiveness data will be collected. Subjects will be interviewed to determine if adverse events (AEs) were experienced since the previous follow-up visit. A complete orthopaedic knee assessment will be performed at baseline for all subjects and again during each follow-up visit. All subjects will be required to complete the KOOS Knee Survey and KSS to evaluate function, pain, and quality of life at each follow-up visit.

Calypso Knee System Clinical Study

Radiographic evaluations will be performed at pre-op, prior to discharge, 6 weeks, 3 months, 6 months, 12 months, 18 months, 24 months and annually thereafter through 5 years for all subjects. Radiographic evaluations will also be performed within 60 days prior to any planned Calypso Knee System removal.

MRI evaluations will be performed at the pre-procedure and at 2 and 5 year follow-up visits.

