4.3 Subsequent Surgical Interventions of the Knee

- **Revision:** A revision is a procedure that adjusts or in any way modifies or removes *part* of the original implant configuration with or without replacement of a component. A revision may also include adjusting the position of the original configuration. This may include removing a component of the device and only replacing that single component.
- **Removal:** A removal is a procedure where all of the original system configuration is removed with or without replacement due to, for example, mechanical failure of the device, pain or infection.
- **Re-operation:** A reoperation is any surgical procedure that does not include removal modification, or addition of any components to the system (e.g., drainage of a hematoma at the surgical site).
- **Supplemental fixation:** A supplemental fixation is a procedure in which additional instrumentation not under study in the protocol is implanted.
- **Other interventions:** This category includes other surgeries of the study knee that the subject incurs while enrolled in the study that seemingly are unrelated to the implanted device.

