5.1 Additional Outcomes

Safety Observations:

- Knee Range of Motion (ROM)
 - Measured passively defined as degrees of flexion and extension
- Adverse Events by type, over time, severity, seriousness, and relatedness
- Subsequent surgical interventions of the knee by type of surgical intervention (revision, removal, re-operation (includes conversion to arthroplasty) supplemental fixation, other intervention)
- Metal ion levels
- In the event of a Calypso Knee System removal, the following assessments will be evaluated:
 - Radiographic evaluations
 - MRI assessment as available
 - Calypso Knee System (implant) retrieval analysis
 - Histology
 - Metal Ion levels
 - Arthroplasty conversion data, if applicable

Effectiveness/Other Observations:

- Patient reported knee outcome measures and activity (KOOS Knee Survey, Activity Questionnaire, SF-12 Health Survey, Patient Satisfaction)
- Investigator reported KSS

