APPENDIX A: DEFINITIONS

ANALGESIC

A pain-relieving effect with no loss of consciousness

BLEEDING COMPLICATION

A procedure related hemorrhagic event that requires a transfusion or surgical repair.

BURSITIS

Bursitis is an inflammation of the native bursae that can result in irritation and pain.

CELLULITIS

A superficial, spreading infection of the skin and subcutaneous tissue, usually following lacerations and surgical wounds. The most common causative organism is penicillin sensitive streptococci. Cellulitis is characterized by signs of inflammation (local pain, tenderness, swelling and erythema). The border between involved and uninvolved skin is usually indistinct and systemic illness characterized by fever, chills, malaise and toxicity is frequently present.

<http://www.who.int/surgery/publications/en/SCDH.pdf>

DEEP VEIN THROMBOSIS

Deep vein thrombosis (DVT) is a blood clot that forms in a vein deep in the body.

Http://www.nhlbi.nih.gov/health/dci/diseases/dvt/dvt_what.html

DEVICE MALFUNCTION

The failure of a device to meet its performance specifications or otherwise perform as intended.

Performance specifications include all claims made in the labeling for the device. (21 CFR Part 803)

DIABETES MELLITUS

A condition caused by insufficient production of insulin resulting in abnormal metabolism of carbohydrates, fats and protein. Diabetes mellitus is defined as symptoms of hyperglycemia (thirst, polyuria, weight loss, visual blurring) and a casual plasma glucose concentration of ≥ 200 mg/dl; or a fasting plasma blood glucose concentration of ≥ 126 mg/dl; or a 2-hour post load glucose ≥ 200 mg/dl during an oral glucose tolerance test as described by the World Health Organization (WHO).

ENROLLED

Subjects who sign informed consent and undergo an anesthesia start time for purposes of receiving the Calypso Knee System.

HEMATOMA

A localized mass of extravasated blood that is relatively or completely confined within an organ or tissue, a space, or a potential space that measures four centimeters or greater in diameter at the vascular access site, or those requiring transfusion or necessitating prolonged hospitalization.

HEMORRHAGE

An escape of blood through ruptured, or unruptured vessel walls.

KNEE SCARRING, ARTHROFIBROSIS, OR PERIPROSTHETIC LOCAL ADHESIONS

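### The 4 cm size criterion for hematoma is tied to a vascular access site, so larger surgical-site hematomas may be under-counted or inconsistently labelled in the by-type adverse event table

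*Combined protocol and SAP*

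**What the plan says.** The HEMATOMA entry in Appendix A describes a confined collection of blood and then sets three alternative criteria. It qualifies if it "measures four centimeters or greater in diameter at the vascular access site", if it needs transfusion, or if it prolongs hospitalization. Only the size criterion names a location.

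The only other visible mention of a hematoma is in section 4.3, where the example of a re-operation is "drainage of a hematoma at the surgical site".

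Appendix A also holds two neighbouring terms. BLEEDING COMPLICATION is "A procedure related hemorrhagic event that requires a transfusion or surgical repair". HEMORRHAGE is "An escape of blood through ruptured, or unruptured vessel walls". Neither sets a size or a site.

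On collection, section 2.1.1 states: "Subjects will be interviewed to determine if adverse events (AEs) were experienced since the previous follow-up visit". On reporting, section 5.1 lists "Adverse Events by type, over time, severity, seriousness, and relatedness" among the safety observations, and the Protocol Summary (Additional Observations Analysis) says "AEs will be tabulated and summarized as counts and percentages".

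**The concern.** A size threshold at a vascular access site suits a procedure done through a vessel. The study device is a knee implant, and the protocol's own example puts the hematoma at the operative wound. If a site applies the definition as written, the 4 cm criterion cannot be met by a hematoma at the study knee, and only transfusion or a longer stay would earn the label.

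At stake is how one local surgical complication of the investigational procedure is reported by type. Up to 10 sites contribute 80 subjects. One site may follow the wording literally, while another reads it as meaning the operated knee. The same event could then appear as a hematoma at one site and under a different term at the next. The intervention table could also show a re-operation for drainage of a hematoma that the AE table does not list under that name.

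**Working it through.** The documents state no hematoma rate or other figure that depends on this definition, so there is no plan figure to reproduce. The check is a comparison of texts.

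**Step 1: the location.** Appendix A ties size to a vascular access site, a term that appears nowhere else in the visible text. Section 4.3 places the hematoma at the surgical site. Both sentences are fully legible, so redaction does not explain the mismatch.

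**Step 2: which surgical-site hematomas of 4 cm or more still qualify.** The size criterion names another site, so it is treated as not met.

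| Surgical-site hematoma of 4 cm or more | HEMATOMA in Appendix A, read literally | Other visible category |
|---|---|---|
| Needs transfusion | Met through the transfusion criterion | BLEEDING COMPLICATION, if procedure related |
| Prolongs hospitalization | Met through the hospitalization criterion | HEMORRHAGE is possible |
| Drained surgically, no transfusion, no longer stay | Not met | Re-operation (section 4.3); BLEEDING COMPLICATION if drainage is read as surgical repair |
| None of these | Not met | HEMORRHAGE or another AE term |

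The gap is confined to the last two rows. For the third row, section 4.3 calls the event a hematoma and Appendix A does not.

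**Step 3: does failing the definition remove the event from the AE count?** No visible text makes an Appendix A definition a condition for reporting or tabulating an AE. Section 2.1.1 has subjects asked about AEs, and the Protocol Summary has AEs tabulated, in neither case with a threshold. What a term definition can change is the type under which the event appears.

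**Step 4: size per event.** Input: 80 subjects to be enrolled (Protocol Summary; section 2.1.1).

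- Change in the hematoma rate per subject whose label changes: 1/80 = 0.0125, or 1.25 percentage points.
- The number of such subjects is not known. As an illustration only: two would give 2/80 = 2.5 points, three 3/80 = 3.75 points.

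This is the weight of any single subject in a study of this size. It is not an estimate of bias.

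**Step 5: endpoints.** The safety components of the primary composite (section 2.4.1) are deep infection requiring surgery, neurovascular or ligament damage requiring reconstruction, and non-union for the comparator. Hematoma is not among them. The five secondary endpoints (section 2.4.2) are time to full weight bearing and WOMAC pain and function changes. None depends on this definition.

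**The case against.** The strongest case against is that this is a wording slip in a mixed glossary. Appendix A also defines terms such as analgesic, diabetes mellitus and screen failure, and nothing visible makes it an operational filter for AEs. Transfusion and prolonged hospitalization carry no site limit, so the more consequential hematomas still qualify. HEMORRHAGE is broad enough to hold the rest, drained cases appear among the surgical interventions, and under section 6.3 serious events go to independent adjudication. The section 4.3 phrase is only an example and does not define hematoma.

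Most of this stands, and it limits the point to labelling. It also answers a stronger reading that a reader might infer: that surgical-site hematomas of 4 cm or more are left out of the AE count altogether. The documents do not support that. No visible rule excludes them. Most of section 4.1 is redacted and the list in section 4.2 is not shown, so an exclusion rule cannot be presumed. Some of these hematomas also meet the definition through the other two criteria.

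The surgical procedure section is redacted too, so the absence of a vascular access site is an inference from the type of device. The conclusion does not need it. Even if there were vascular access, for example for the metal ion blood draws, a criterion located there would still not reach a hematoma at the knee.

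The objection does not remove the mismatch. A surgical-site hematoma of 4 cm or more without transfusion or a longer stay fails the written definition, and falling back on HEMORRHAGE would spread the same kind of event over several labels.

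**Conclusion.** The mismatch is real and its consequence is minor. Read literally, the size criterion cannot capture a surgical-site hematoma. Those of 4 cm or more with neither transfusion nor prolonged hospitalization may therefore be under-counted or inconsistently classified in the by-type AE table. Each such subject is worth 1.25 percentage points of the reported hematoma rate; how many there would be cannot be judged from the documents. Nothing visible shows a loss from the overall AE count, and the primary and secondary endpoints are not affected.

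This rests on two assumptions: that sites or coders use Appendix A when assigning the AE type, and that no redacted text redefines the site for this study.

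**What to change.** - Reconcile Appendix A with section 4.3, so that the site wording in the HEMATOMA entry refers to the surgical site (study knee). Leave the 4 cm, transfusion and hospitalization criteria unchanged.
- State whether Appendix A governs only the coding of AE type or also whether an event is reported. The site wording alone does not settle this. A drained hematoma under 4 cm with no transfusion or longer stay would still fall outside the definition, so the protocol should make clear how such an event is labelled.
- Re-check the type coding of hematoma and bleeding events already recorded against the corrected entry.

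The cost is a one-phrase correction, one clarifying sentence and a small re-coding check. The reported hematoma rate may become slightly less favourable.
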